2.2.2 Pharmacokinetic Endpoints

• Blood samples will be collected on dosing days (pre-dose and at 30 minutes (+ 15 minutes) and 4 hours (±20 minutes) following the initiation of study drug infusion) and at the follow-up visits. The following PK parameters will be calculated: C_{max}, T_{max}, C_{avg}, C_{min}, and t_{1/2}. Additional standard and exploratory PK parameters will be calculated if deemed necessary.

2.2.3 Pharmacodynamic Endpoints

- Fecal calprotectin change from Day 0 (baseline) to all scheduled measurement timepoints.
- Change in eosinophil count, serum eotaxin-1,hs-CRP and ECP from Day 0 to all scheduled measurement timepoints.
- Change in eotaxin-1 concentration and eosinophil count in biopsy tissue from Screening to Day 56.

2.2.4 Safety Endpoints

Safety will be evaluated on the basis of the following parameters:

- Adverse events (AE)
- Infusion reactions
- Physical examination
- Vital signs (blood pressure, heart rate, temperature and respiratory rate)
- ECG
- Concomitant medications
- Laboratory evaluation (hematology, biochemistry, anti-bertilimumab antibodies).

3. STUDY DESIGN

This is a randomized, double blind, placebo-controlled, parallel group multi-center study in adult patients with active moderate to severe UC^h. Eligible subjects will be randomly assigned in a 2:1 ratio to one of two treatment groups, bertilimumab 10 mg/kg or matching placebo, stratified by previous anti-TNF treatment. Approximately the same proportion of subjects who received previous anti-TNF treatment will be included in each arm. The study

Protocol: Immune/BRT/UC-01 Page 21 of 58 Final Version 8.0 May 23, 2018

^h A Mayo Score of 6 to 12 (inclusive); Endoscopic evidence of active ulcerative colitis (i.e., Endoscopic Finding Sub-score of ≥2) as assessed by flexible sigmoidoscopy unless colonoscopy is clinically indicated; Rectal Bleeding Sub-score of ≥1; Physician's Global Assessment (PGA) of at least moderate disease (Mayo Sub-score ≥2).

will consist of three periods: a screening period of up to four weeks, a 4-week double-blind treatment period (three IV infusions at two-week intervals), and a safety and efficacy follow-up period of approximately 9 weeks. A schedule of events for this study is shown in Appendix A. The total duration of subject participation will be \sim 16-19 weeks. The study will be conducted in up to 10-12 sites in Israel. Additional sites in Europe may be added in the event of slow recruitment.

4. STUDY POPULATION

The study will be conducted in patients aged 18 to 70 years diagnosed with active moderate to severe UC. Subjects who meet all of the inclusion criteria and none of the exclusion criteria will be randomized to treatment groups.

4.1 INCLUSION CRITERIA

- 1. Males or females, 18 to 70 years of age inclusive.
- 2. Diagnosed with active moderate to severe UC per standard diagnostic criteria for a minimum of 3 months. The subject must present with the following at the screening visit:
 - Mayo score of 6-12 (inclusive).
 - Endoscopic evidence of active mucosal disease, as assessed by flexible sigmoidoscopy, with an Endoscopic Finding Sub-score of ≥2 (assessed centrally).
 - Rectal Bleeding Sub-score of ≥1.
 - Physician's Global Assessment (PGA) Sub-score of ≥2.
- 3. Levels of eotaxin-1 in biopsied colon tissue of ≥50 pg/mg protein.
- 4. Adequate cardiac, renal and hepatic function as determined by the Investigator and demonstrated by screening laboratory evaluations and physical examination results; these findings must all be within normal limits or judged not clinically significant by the Investigator.
- 5. Females of childbearing potential must agree to use effective contraception consistently throughout the study (such as hormonal contraception or two forms of barrier contraception) and have a negative serum pregnancy test at screening and a negative urine pregnancy test before administration of each study treatment.
- 6. Males of childbearing potential must agree to use effective contraception consistently throughout the study and a period of four months following the end of the study treatment-
- 7. Willing and able to adhere to the study visit schedule and other protocol requirements.
- 8. Willing and able to provide voluntary written informed consent.

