Planned Sample Size	Up to 42 subjects are planned to be recruited to this study, randomized to the two arms using a 2:1 active drug to placebo ratio and stratified by previous anti-TNF treatment. Investigators are encouraged to recruit subjects who have not received previous anti-TNF treatment.
Inclusion Criteria	1. Males or females, 18 to 70 years of age inclusive.
	2. Diagnosed with active moderate to severe UC per standard diagnostic criteria for a minimum of 3 months The subject must present with the following at the screening visit:
	Mayo score of 6-12 (inclusive).

 $^{^{\}rm c}$ Visits 3 and 4 during the Treatment Period have a ± 2 day window.

 $^{^{\}rm d}$ Visits during the Follow-Up Period have a ± 3 day window.

- Endoscopic evidence of active mucosal disease, as assessed by flexible sigmoidoscopy, with an Endoscopic Finding Sub-score of ≥2 (assessed centrally).
- Rectal Bleeding Sub-score of ≥ 1 .
- Physician's Global Assessment (PGA) Sub-score of ≥2.
- 3. Levels of eotaxin-1 in biopsied colon tissue of \geq 50 pg/mg protein.
- 4. Adequate cardiac, renal and hepatic function as determined by the Investigator and demonstrated by screening laboratory evaluations and physical examination results; these findings must all be within normal limits or judged not clinically significant by the Investigator.
- 5. Females of childbearing potential must agree to use effective contraception consistently throughout the study (such as hormonal contraception or two forms of barrier contraception) and have a negative serum pregnancy test at screening and a negative urine pregnancy test before administration of each study treatment.
- 6. Males of childbearing potential must agree to use effective contraception consistently throughout the study and for a period of four months following the last treatment
- 7. Willing and able to adhere to the study visit schedule and other protocol requirements.
- 8. Willing and able to provide voluntary written informed consent.

Exclusion criteria

- 1. History of colonic or rectal surgery other than hemorrhoidal surgery or appendectomy.
- 2. Currently receiving total parenteral nutrition (TPN).
- 3. Positive Clostridium difficile toxin stool assay.
- 4. Tested positive for active/latent mycobacterium tuberculosis (TB) infection.
- 5. Pregnant or breast-feeding, or plan to become pregnant during the study.

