1.3.1 Rationale for Dose Selection

Immune Pharmaceuticals has chosen to evaluate an IV dose of 10 mg/kg bertilimumab every 2 weeks based on the following safety, PK and PD data:

- No safety concerns were identified in Study CAT-213-0101, in which subjects received a single IV bertilimumab dose of up to 10 mg/kg (corresponding to absolute doses of 570 to 770 mg in four subjects), or in Study CAT-213-0103, in which subjects received a single IV bertilimumab dose of up to 500 mg.
- The PD endpoint in Study CAT-213-0101, eotaxin-induced eosinophil shape change, was inhibited by serum from all subjects who received bertilimumab doses of 1 mg/kg and higher, with nearly 100% inhibition in the 5 mg/kg and 10 mg/kg dose groups. A shape change in eosinophils is considered a requisite process in chemotaxis, and can be taken as evidence of an impending migratory response. Maximum inhibition occurred at concentrations of ~40 μg/mL. At 35 days post-dose, high levels of inhibition were still observed despite low concentrations of bertilimumab, suggesting that the PD response was prolonged when compared with the bertilimumab plasma concentrations.
- In Study CAT-213-001, after a single dose of 5 mg/kg, unbound bertilimumab had a mean half-life of 211 hours (CV% 30.5); the mean half-life after a single 10 mg/kg

dose was 194 hours (CV% 27.1). The half-life of total bertilimumab (bound plus unbound) is estimated to be 16-20 days. The data from this study also suggest dose proportionality in bertilimumab exposure between these two doses.

• No antibodies to bertilimumab were detected in any of the three previous single-dose clinical trials.

Systemic markers of bertilimumab activity (peripheral blood eosinophil count, serum levels of eotaxin-1, ECP, and hs-CRP), as well as eosinophil count and eotaxin level in intestinal tissue, and their correlation with the therapeutic response in UC patients will be also assessed.

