4.5 REMOVAL, REPLACEMENT, OR EARLY DISCONTINUATION OF SUBJECTS FROM THERAPY OR ASSESSMENT

Subjects are free to discontinue their participation in the study at any time and without prejudice to further treatment. The Investigator must withdraw any subject from the study if that subject requests to be withdrawn, or if it is determined that continuing in the study would result in a significant safety risk to the subject. Withdrawn subjects will not be replaced.

The subject's participation in this study may be discontinued due to the following reasons:

- Subject withdraws consent.
- Intolerable adverse event (any subject experiencing a grade 3 or 4 infusion reaction will be withdrawn from the study).
- Subject's need for medication prohibited by the protocol.

- The Investigator decides that continuing in the study would not be in the subject's best interest.
- The subject is noncompliant with the protocol.
- The subject becomes pregnant.
- Upon the decision of relevant Regulatory Authorities and/or the Institutional Review Board/Independent Ethics Committee (IRB/IEC).

Subjects who progress and/or relapse will be withdrawn from the study at the Investigator's discretion and will be able to receive local standard-of-care.

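### Women of childbearing potential have no fixed contraception period after the last infusion, so an early withdrawal has no guaranteed cover, while men have four months

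*Protocol*

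**What the plan says.** Criterion 5, in the Protocol synopsis and in section 4.1, reads "Females of childbearing potential must agree to use effective contraception consistently throughout the study". It adds the pregnancy-test requirements and gives no duration beyond the study.

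Criterion 6 requires men to use contraception during the study and for "a period of four months following the end of the study treatment" (section 4.1), or "for a period of four months following the last treatment" (synopsis). No reason is given for treating the sexes differently.

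On leaving early, section 4.5 states "Subjects are free to discontinue their participation in the study at any time". It also makes a grade 3 or 4 infusion reaction a cause for mandatory withdrawal from the study. Section 4.5.1 asks for every effort at safety follow-up, and section 5.4 describes an early discontinuation visit. Neither mentions contraception.

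Two other safeguards bear on pregnancy. Exclusion criterion 5 rules out women who plan a pregnancy, but only while the study lasts. Section 5.6.7 places pregnancy tests at screening and before each infusion. The SAP does not mention contraception.

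**The concern.** Men have a fixed period that runs from treatment and does not depend on how long they stay in the trial. Women, who can become pregnant while carrying the drug, have a duty that depends entirely on remaining in the study. The protocol foresees several early exits: withdrawn consent, relapse, need for prohibited medication, and severe infusion reactions. The last of these happen during or within hours of a dose, when drug levels are near their highest.

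A woman who leaves early and follows the criterion exactly could stop contraception with much of the drug still in her circulation. The pharmacological effect may also outlast the measurable drug. For the earlier single-dose study, section 1.3.1 reports: "At 35 days post-dose, high levels of inhibition were still observed despite low concentrations of bertilimumab". The stake is participant safety. Sample size, power and alpha are untouched.

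**Working it through.** **Inputs (all from the Protocol)**

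- Last infusion Day 28 (±2 days); last visit Day 90 (±3 days): section 1.3.
- Follow-up period 62 days (±9 days); total duration about 118 days: synopsis.
- Half-life of total drug: "The half-life of total bertilimumab (bound plus unbound) is estimated to be 16-20 days" (section 1.3.1).
- Mean half-life of unbound drug: 194 h at 10 mg/kg (CV 27.1%) and 211 h at 5 mg/kg (CV 30.5%), section 1.3.1. In days, 194/24 = 8.08 and 211/24 = 8.79.

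**Reproducing the plan's own figures.** 90 − 28 = 62 days, as stated. 28 (screening) + 28 (treatment) + 62 = 118 days, also as stated. The two visit windows alone give (90 − 3) − (28 + 2) = 57 days to (90 + 3) − (28 − 2) = 67 days.

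**Length of cover after the last infusion**

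| Subject | Guaranteed cover |
|---|---|
| Woman, completes | about 62 days (57-67 by visit windows) |
| Woman, withdraws early (literal reading) | 0 days |
| Man, completes or not | four months, about 122 days |

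The difference between a man and a completing woman is 122 − 62 = 60 days.

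**Drug remaining.** The share of the post-dose level after t days is 0.5^(t / half-life), assuming first-order decline. For example, total drug at 14 days is 0.5^(14/16) = 54.5% to 0.5^(14/20) = 61.6%. Unbound drug at 14 days is 0.5^(14/8.08) = 30.1% to 0.5^(14/8.79) = 33.2%.

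| Days after last infusion | Total drug (16-20 d) | Unbound drug (194-211 h) |
|---|---|---|
| 7 | 73.8-78.5% | 54.9-57.6% |
| 14 | 54.5-61.6% | 30.1-33.2% |
| 28 | 29.7-37.9% | 9.1-11.0% |
| 62 (completer) | 6.8-11.7% | 0.49-0.75% |
| 57-67 (completer, with windows) | 5.5-13.9% | 0.32-1.12% |
| 122 (four months) | 0.5-1.5% | <0.01% |

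The 7-, 14- and 28-day rows are illustrative, because the documents set no interval between the last dose and the discontinuation visit. Fourteen days is one dosing interval, for instance a woman who leaves at Visit 3 or 4 before that day's infusion. A stopped infusion lowers the starting level but not these fractions. For a completer, 62 days is 62/20 = 3.1 to 62/16 = 3.9 half-lives of total drug.

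**Sensitivity to the reported variation.** Moving the unbound half-life one CV either way gives 194 × (1 − 0.271) = 141 h (5.89 d) at the low end and 211 × (1 + 0.305) = 275 h (11.47 d) at the high end. At 14 days the unbound share is then 0.5^(14/5.89) = 19% to 0.5^(14/11.47) = 43%.

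**The case against.** The strongest reply is that the gap rests on one reading. The study could mean the planned course to Day 90. The synopsis gives a per-subject duration, section 8.3.2 says enrolled subjects are followed to completion, section 8.3.7 runs the safety observation period to Day 90, and section 4.5.1 presses for safety follow-up. On that reading a woman who withdraws keeps her duty to Day 90. But section 4.5 speaks of withdrawal from the study itself, and no text tells a withdrawn woman that her duty continues. The ambiguity is real, which is why the point is that cover is not guaranteed, rather than that it is certainly absent.

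Other points carry some weight:

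- A urine test may fall within the discontinuation visit. Section 5.4 points a subject leaving during treatment to section 5.2, which lists one, although Appendix A does not mark it there. A test that day sets no duty afterwards.
- The consent form and the Investigator's Brochure were not available and may say more. The criterion neither states nor refers to a longer period.
- No reproductive hazard, exposure threshold or washout standard appears in the documents, and the 35-day result concerns eosinophil shape change. This limits the claim to a precaution.
- The men's rule grew out of relaxing a male-specific exclusion, as the version history shows. Nothing shows that four months was chosen for clearance, or that it is the right period for women. It is a default, open to a justified alternative.
- The decay figures come from single-dose data and ignore any distribution phase, which would make them too high. The total-drug half-life is itself an estimate.
- The affected group is small: at most 42 subjects, about 28 on active drug, and among them only women of childbearing potential who leave early and stop contraception promptly. The documents give no rate for this.

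None of these gives a woman who withdraws a stated period of cover.

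**Conclusion.** The concern holds. As written, a woman of childbearing potential has no contraception period tied to her last infusion. If she withdraws early, her guaranteed cover on a literal reading is zero days, with roughly 74-78% of total drug remaining at 7 days and 55-62% at 14 days (unbound: 55-58% and 30-33%). For completers the point is only a caution. They have about 62 days of cover, with under 1% of unbound drug left on the mean half-lives and nominal visit days, and the documents state no rule that this breaches.

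The sizes assume first-order decline from the post-dose level at the half-lives in section 1.3.1. The conclusion on the wording does not depend on them. This is a change the sponsor should make for participant safety, at little cost. It has no bearing on the validity of the efficacy results.

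**What to change.** Reword criterion 5 in section 4.1 and the synopsis so that women of childbearing potential use effective contraception during the study and for a fixed period after the last infusion, whether or not they complete the study. Use the four months already set for men unless the sponsor's clinical team justifies another duration. By 122 days the calculation leaves about 0.5-1.5% of total drug. Add a reminder of this duty to the early discontinuation visit in section 5.4, and check that the consent form says the same.

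The cost is protocol and consent wording, with no added visits or data. The downside is a longer contraception commitment for women: about 60 days more for a completer if four months is adopted.

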4.2 EXCLUSION CRITERIA

- 1. History of colonic or rectal surgery other than hemorrhoidal surgery or appendectomy.
- 2. Currently receiving total parenteral nutrition (TPN).
- 3. Positive *Clostridium difficile* toxin stool assay.
- 4. Tested positive for active/latent mycobacterium tuberculosis (TB) infection.
- 5. Pregnant or breast-feeding, or plan to become pregnant during the study.
- 6. Known hypersensitivity to bertilimumab or any of the drug excipients or to any components of the pretreatment regimens.

- 7. History of infection requiring administration of any IV antibiotic, antiviral or antifungal medication within 30 days of Screening or any oral anti-infective agent within 14 days of Screening.
- 8. Acute or fulminant UC requiring immediate surgery or severe UC evidenced by the following signs of toxicity: toxic megacolon, abscess, heart rate >100 beats/min at rest, temperature >38.2°C, hemoglobin <8.0 g/dL.
- 9. Ulcerative proctitis, defined as disease limited to less than 15 cm from the anal verge.
- 10. Received a vaccine or other immunostimulator within 4 weeks prior to screening.
- 11. Use of>4.8 g mesalazine or equivalent within 2 weeks prior to the screening visit. Mesalazine ≤4.8 g is allowed if the dose during the 2 weeks prior to the screening visit was stable.
- 12. Use of systemic corticosteroids exceeding the equivalent of 20 mg/day of prednisone (see Section 6.9.1) within four weeks prior to the screening visit.
- 13. Change in dose of immunosuppressive drugs (e.g., corticosteroids, 6-MP, azathioprine) within four weeks prior to the screening visit.
- 14. Use of TNF-blockers (e.g., infliximab, adalimumab) within 60 days of the screening visit
- 15. Use of integrin blockers (e.g., vedolizumab) within 60 days of the screening visit.
- 16. Use of chronic non-steroidal anti-inflammatory (NSAID) therapy. Occasional use of NSAID and acetaminophen for headache, arthritis, myalgias, menstrual cramps etc., daily use of low-dose (81-162 mg) aspirin for cardiovascular prophylaxis is permitted.
- 17. Subject diagnosed with:
 - Crohn's disease
 - Diverticulitis or diverticulosis
 - Indeterminate colitis (inability to distinguish between UC and Crohn's disease [as assessed by the Investigator])
 - Microscopic colitis (collagenous or lymphocytic colitis)
 - Ischemic or infectious colitis
 - Clostridium difficile colitis within 90 days of the screening visit
 - Parasitic disease within 90 days of the screening visit
 - Systemic fungal infection within 90 days of the screening visit.
- 18. Current or history of positive serology of hepatitis B or C, or human immunodeficiency virus (HIV) infection.
- 19. Congenital or acquired immunodeficiency (e.g., common variable immunodeficiency, organ transplantation).
- 20. Clinically significant abnormal laboratory test results, unless regarded by the Investigator as related to UC, including but not limited to:
 - Hemoglobin level < 10.0 g/dL
 - White blood cell count $< 3 \times 10^3/\mu$ L
 - Lymphocyte count $< 0.5 \times 10^3/\mu L$
 - Platelet count $< 100 \text{ x } 10^3/\mu\text{L or} > 1200 \text{ x } 10^3/\mu\text{L}$
 - Alanine aminotransferase (ALT) or aspartate aminotransferase (AST) > 3 \times the upper limit of normal (ULN)

- Alkaline phosphatase >3 × ULN
- Serum creatinine > 2 × ULN.
- 21. Active abuse of alcohol or drugs.
- 22. Known malignancy or history of malignancy that could reduce life expectancy.
- 23. Any condition, which in the opinion of the Investigator, would place the subject at an unacceptable risk if participating in the study protocol.
- 24. Participation in a clinical trial of an investigational (unapproved) product within 1 month of the screening visit.

4.3 Subject Identification and Treatment Allocation

At screening, all subjects who signed informed consent will be identified by a screening number, their initials and birth date. Subjects who meet all inclusion criteria and none of the exclusion criteria will be randomized to treatment groups. Subjects will be block randomized centrally (i.e., not within each center) and stratified by previous anti-TNF treatment. Specifically, the randomization scheme will ensure that approximately equal proportions of subjects who received previous anti-TNF treatment will be in each of the two treatment arms.

The randomization list specifying treatment assignments will be generated by the Clinical Research Organization (CRO). Within each anti-TNF treatment strata, each eligible subject will be assigned a treatment corresponding to the randomization number specified on the randomization list in the order in which they are enrolled; i.e. separate block randomization sequences will be generated for each anti-TNF strata and each subject will be given a randomization number in sequence within his or her strata. The randomization number assigned to the subject will be recorded by the pharmacist on the infusion bag when the dose is prepared.

In the event of a medical emergency requiring knowledge of the study drug assignment, the Investigator will be provided access to the randomization code in the secured database by the data management team.

4.4 SCREENING FAILURES

Subjects who fail to meet the eligibility criteria at any stage prior to randomization are defined as screen failures. All screen failures will be documented on the screening log, which documents the screening number, subject's initials, birth date and reason(s) for screen failure. The screening log will be kept in the Investigator's Site File. Screen failure subjects will not be enrolled in the study and will receive the local standard-of-care.

4.5 REMOVAL, REPLACEMENT, OR EARLY DISCONTINUATION OF SUBJECTS FROM THERAPY OR ASSESSMENT

Subjects are free to discontinue their participation in the study at any time and without prejudice to further treatment. The Investigator must withdraw any subject from the study if that subject requests to be withdrawn, or if it is determined that continuing in the study would result in a significant safety risk to the subject. Withdrawn subjects will not be replaced.

The subject's participation in this study may be discontinued due to the following reasons:

- Subject withdraws consent.
- Intolerable adverse event (any subject experiencing a grade 3 or 4 infusion reaction will be withdrawn from the study).
- Subject's need for medication prohibited by the protocol.

- The Investigator decides that continuing in the study would not be in the subject's best interest.
- The subject is noncompliant with the protocol.
- The subject becomes pregnant.
- Upon the decision of relevant Regulatory Authorities and/or the Institutional Review Board/Independent Ethics Committee (IRB/IEC).

Subjects who progress and/or relapse will be withdrawn from the study at the Investigator's discretion and will be able to receive local standard-of-care.

